7.2.2 Reporting of Pregnancy and Lactation to the Sponsor

Although pregnancy and lactation are not considered adverse events, it is the responsibility of investigators or their designees to report any pregnancy or lactation in a subject (spontaneously reported to them), including the pregnancy of a male subject's female partner that occurs during the trial.

Pregnancies and lactations of subjects and female partners of male subjects from the time the consent form is signed but before treatment allocation/randomization must be reported by the investigator if they cause the subject to be excluded from the trial, or are the result of a protocol-specified intervention, including but not limited to washout or discontinuation of usual therapy, diet, placebo treatment or a procedure. Pregnancies and lactations of subjects and female partners of male subjects that occur from the time of treatment allocation/randomization through 14 days following cessation of Sponsor's product must be

reported. All reported pregnancies must be followed to the completion/termination of the pregnancy. Pregnancy outcomes of spontaneous abortion, missed abortion, benign hydatidiform mole, blighted ovum, fetal death, intrauterine death, miscarriage and stillbirth must be reported as serious events (Important Medical Events). If the pregnancy continues to term, the outcome (health of infant) must also be reported.

Such events must be reported within 24 hours to the Sponsor either by electronic media or paper. Electronic reporting procedures can be found in the EDC data entry guidelines. Paper reporting procedures can be found in the Investigator Trial File Binder (or equivalent).

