5.7.2.5 Contraception

Male subjects with female partner(s) of child-bearing potential must agree to use a medically acceptable method of contraception during the trial and for 90 days after the last dose of trial drug. Males should use a condom. Female partners must additionally use one of the following methods if they are not pregnant: hormonal contraception, intra-uterine device, diaphragm, or cervical cap. If their partner is pregnant, males must agree to use a condom and no additional method of contraception is required for the pregnant partner. Male subjects must also agree to not donate sperm during the study and for a period of 90 days after the last dose of study drug.

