7.1.5.2 Treatment Period Visit

Subcutaneous MK-5160 or glargine will be administered as a daily injection from Day 1 to Day 12.

Exogenous glucose will also be infused concurrently with adjustments as needed to maintain a stable glucose concentration predefined by the subject's baseline fasting glucose during the clamp procedure and longer if necessary. Details of this euglycemic clamp technique are outlined in the Study Operations Manual.

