7.1.5.3 Post-Trial

Subjects will be required to return to clinic approximately 16 days (+/ 3 days) after the last dose of trial drug for the post-trial visit. If the post-trial visit occurs less than 16 days after the last dose of trial drug, a subsequent follow-up phone call should be made at 16 days post the last dose of trial drug to determine if any adverse events have occurred since the post-trial

clinic visit. Subjects will be required to return to clinic approximately 16 days (+/- 3 days) post final dose (Day 28) for collection of additional anti-drug antibodies (ADA) and anti-insulin antibodies (AIA) samples.

If a subject has a positive titer at the 28 day follow-up visit, an additional sample will be drawn approximately 56 days (+/- 5 days) after the completion of dosing. At the same time, a fasting plasma glucose sample will be drawn from the subject and an evaluation of possible signs and symptoms of hyperglycemia will be conducted. If medically required the subject will be referred to an endocrinologist for further treatment.

Additional follow-ups will be conducted in intervals of approximately 3 months (+/- 5 days) in subjects with detectable ADAs/AIAs until one of the following occurs:

- a) subject no longer has detectable ADAs/AIAs,
- b) ADAs/AIAs are persistent and stable (titers within 2 to 3-fold of each other) on 3 consecutive checks at 3 month intervals,
- c) return to baseline levels (i.e., within 2 to 3-fold of predose)

An additional fasting plasma glucose sample will be drawn at each time subjects return for ADA/AIA follow-up, and an evaluation of possible signs and symptoms of hyperglycemia will be conducted. Subjects will be referred to an endocrinologist if medically required.

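### The explicit window for reporting partner pregnancies ends 14 days after dosing, while the contraception rule for male subjects runs for 90 days

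*Combined protocol and SAP*

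**What the plan says.** Section 5.7.2.5 (Contraception) says that male subjects whose partners could become pregnant "must agree to use a medically acceptable method of contraception during the trial and for 90 days after the last dose of trial drug". It bars sperm donation during the study and "for a period of 90 days after the last dose of study drug".

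Section 7.2.2 (Reporting of Pregnancy and Lactation to the Sponsor) has three relevant parts.

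- It opens with a general duty to report any pregnancy that the investigator is told of, "including the pregnancy of a male subject's female partner that occurs during the trial". No day count is given.
- For the time after randomization it then gives an explicit limit: "Pregnancies and lactations of subjects and female partners of male subjects that occur from the time of treatment allocation/randomization through 14 days following cessation of" the Sponsor's product must be reported.
- Every reported pregnancy is followed to its end, and losses such as miscarriage and stillbirth are to be reported as serious.

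The same section states that pregnancy is not an adverse event. Inclusion criterion 2 in Section 5.1.2 admits only women of non-childbearing potential, in both parts of the trial.

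**The concern.** The plan holds men to a reproductive precaution for 90 days after dosing but sets an explicit duty to report partner pregnancies for only the first 14 of those days. Nothing in the protocol extends the window or explains the difference. Since the women enrolled cannot, by the entry criteria, be expected to conceive, partner pregnancies are essentially the only events Section 7.2.2 can collect.

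What is at stake is safety information on a new agent in an early multiple-dose trial. Take a partner pregnancy that begins on Day 40. It falls within the contraception period but outside the explicit reporting limit. If the site does not report it, the follow-up to outcome in 7.2.2 is not triggered, because that follow-up applies to reported pregnancies.

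**Working it through.** The plan states no figure to reproduce, so the check is a count of days.

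**Inputs**

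- Last dose, Section 7.1.5.2: "Subcutaneous MK-5160 or glargine will be administered as a daily injection from Day 1 to Day 12". The last dose is therefore on Day 12.
- Explicit pregnancy window, Section 7.2.2: 14 days after cessation.
- Contraception and sperm-donation period, Section 5.7.2.5: 90 days after the last dose.
- Post-trial visit, Section 7.1.5.3: about 16 days after the last dose, plus or minus 3 days (nominal Day 28).
- Adverse event window, Section 7.2: 19 days after cessation, with a parenthesis placing it 5 days after Day 28.

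**Main result**

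- Reporting closes: 12 + 14 = Day 26.
- Contraception period closes: 12 + 90 = Day 102.
- Days outside the window: 90 − 14 = 76.
- Share: 76 / 90 = 84.4%.

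**Does another reading remove the gap?** With a window of w days after the last dose, the uncovered share is (90 − w) / 90.

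| Reading of the window | w | Ends on | Uncovered days | Share of 90 |
|---|---|---|---|---|
| Explicit limit in 7.2.2 | 14 | Day 26 | 76 | 84.4% |
| General duty in 7.2.2, if a subject's trial ends at the Day 28 visit | 16 | Day 28 | 74 | 82.2% |
| Adverse event window borrowed, 19 days | 19 | Day 31 | 71 | 78.9% |
| Adverse event window borrowed, 5 days after Day 28 | 21 | Day 33 | 69 | 76.7% |

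Adding the 12 dosing days to the period at issue gives 76 / (12 + 90) = 76 / 102 = 74.5%. On each of these readings most of the period is uncovered. The one reading that could remove much of the gap takes the trial to mean the whole study. It is dealt with under the objection.

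**Do other reporting rules fill the gap?**

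- Section 7.2.3.1 keeps serious adverse events reportable outside the window if they are judged related and come to the investigator's attention. Table 7 counts a congenital anomaly in a treated subject's offspring as serious whenever it is diagnosed. Together these keep a related anomaly reportable.
- They do not reach the pregnancy itself, which is not an adverse event, or an anomaly judged unrelated. Miscarriage and stillbirth are made serious within the scheme of 7.2.2, as outcomes of a reported pregnancy.
- The antibody sample at about 56 days after dosing (Section 7.1.5.3) applies only to subjects with a positive titer. It is an occasion for contact and does not extend the reporting window.

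**The case against.** Five points on the other side deserve weight.

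1. **Outcomes are not all lost.** A reader might infer that every outcome after Day 26 disappears. Section 7.2.3.1 and Table 7 do not support that, because a related anomaly stays reportable at any time. This stands and narrows the gap to later pregnancies, their non-anomaly outcomes and anomalies judged unrelated.

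2. **The text does not tell sites to stay silent.** A reader might infer that a site is instructed not to report a later partner pregnancy. The opening duty in 7.2.2 stands against that. Section 5.10 ends the overall trial at the last subject's last contact, and Section 1.0 estimates about 8 months. If the trial means the whole study, many subjects' 90 days would fall partly or wholly inside it. On a per-subject reading the duty ends near Day 28, and 5.7.2.5 leans that way, since it adds 90 days after the last dose to the time of the trial. The text is unclear, which supports clarifying it.

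3. **The window turns on when a pregnancy occurs.** A reader might argue that a conception near the last dose is missed because it is noticed late. Section 7.2.2 covers pregnancies that occur within the window, so such a pregnancy is covered whenever it is recognised. The nominal Day 28 visit, which may fall between Day 25 and Day 31, does not itself create a gap.

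4. **The protocol names no reproductive risk period.** Section 5.7.2.5 sets a contraception and sperm-donation rule, and the available text gives no toxicological reason for the 90 days. Nor does it say that the reporting and contraception periods must be equal. This stands: the case for aligning them rests on consistency with the plan's own precaution.

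5. **Few events are expected, and some material is unseen.** Section 5.7.2.5 requires a condom, plus a second method for partners who are not already pregnant. The consent pages are not available, so whether men are already asked to report later partner pregnancies cannot be checked. Both points limit the weight of the concern but leave the wording of 7.2.2 as it is.

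**Conclusion.** The mismatch is real and explicit: Day 26 against Day 102, or 76 of 90 days. The 84% counts calendar days. It should not be read as a share of risk or of expected pregnancies, because the documents give no basis for weighting the days.

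Within those 76 days, the pregnancies themselves, outcomes such as miscarriage or stillbirth, and anomalies judged unrelated are not clearly reportable. The conclusion assumes that dosing ends on Day 12 as planned and that the explicit 14-day limit governs where the undated opening duty leaves doubt. If that duty were read as running to the end of the whole study, the gap would be smaller and would vary with each subject's enrolment date.

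This is a modest gap in safety capture that is worth closing. It does not touch the primary analysis or the sample size, and it implies no view on how long contraception should last.

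**What to change.** Reconcile Sections 5.7.2.5 and 7.2.2. In 7.2.2, make pregnancies of female partners of male subjects reportable if they occur from randomization through the end of the contraception period stated in 5.7.2.5 (currently 90 days after the last dose). Tying the window to that section keeps the two aligned if the period is ever changed. Leave the follow-up to outcome as it stands, and have the opening sentence of 7.2.2 refer to the same period. At the existing Day 28 visit, remind male subjects to tell the site of a partner pregnancy in that period, and check that the consent text and subject card agree.

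On the current figures the window would close on Day 102 instead of Day 26, and the uncovered days would fall from 76 to 0. The cost is a short text change with no new visit. A few reports may arrive after a subject's last visit, and following a partner's pregnancy may need her agreement because she is not a trial subject.

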7.2.3 Immediate Reporting of Adverse Events **Adverse Events and Incidents to the Sponsor**

7.2.3.1 Serious Adverse Events

A serious adverse event is any adverse event occurring at any dose or during any use of Sponsor's product that:

- Results in death;
- Is life threatening;
- Results in persistent or significant disability/incapacity;
- Results in or prolongs an existing inpatient hospitalization;
- Is a congenital anomaly/birth defect;
- Is an other important medical event.

Note: In addition to the above criteria, adverse events meeting either of the below criteria, although not serious per ICH definition, are reportable to the Sponsor in the same timeframe as SAEs to meet certain local requirements. Therefore, these events are considered serious by the Sponsor for collection purposes.

- Is a cancer;
- Is associated with an overdose.

Refer to [Table 7](#) for additional details regarding each of the above criteria.

For the time period beginning when the consent form is signed until treatment allocation/randomization, any serious adverse event, or follow up to a serious adverse event, including death due to any cause, that occurs to any subject must be reported within 24 hours to the Sponsor if it causes the subject to be excluded from the trial, or is the result of a protocol-specified intervention, including but not limited to washout or discontinuation of usual therapy, diet, placebo treatment or a procedure.

For the time period beginning at treatment allocation/randomization through 19 days following cessation of treatment (5 days after Day 28), any serious adverse event, or follow up to a serious adverse event, including death due to any cause, whether or not related to the Sponsor's product, must be reported within 24 hours to the Sponsor either by electronic media or paper. Electronic reporting procedures can be found in the EDC data entry guidelines. Paper reporting procedures can be found in the Investigator Trial File Binder (or equivalent).

Additionally, any serious adverse event, considered by an investigator who is a qualified physician to be related to the Sponsor's product that is brought to the attention of the investigator at any time outside of the time period specified in the previous paragraph also must be reported immediately to the Sponsor.

All subjects with serious adverse events must be followed up for outcome.

7.2.3.2 Events of Clinical Interest

Selected non-serious and serious adverse events are also known as Events of Clinical Interest (ECI) and must be reported to the Sponsor.

For the time period beginning when the consent form is signed until treatment allocation/randomization, any ECI, or follow up to an ECI, that occurs to any subject must be reported within 24 hours to the Sponsor if it causes the subject to be excluded from the trial, or is the result of a protocol-specified intervention, including but not limited to washout or discontinuation of usual therapy, diet, placebo treatment or a procedure.

For the time period beginning at treatment allocation/randomization through 14 days following cessation of treatment, any ECI, or follow up to an ECI, whether or not related to the Sponsor's product, must be reported within 24 hours to the Sponsor, either by electronic media or paper. Electronic reporting procedures can be found in the EDC data entry guidelines. Paper reporting procedures can be found in the Investigator Trial File Binder (or equivalent).

Events of clinical interest for this trial include:

1. an overdose of Sponsor's product, as defined in Section 7.2.1 - Definition of an Overdose for This Protocol and Reporting of Overdose to the Sponsor, that is not associated with clinical symptoms or abnormal laboratory results.
2. an elevated AST or ALT lab value that is greater than or equal to 3X the upper limit of normal and an elevated total bilirubin lab value that is greater than or equal to 2X the upper limit of normal and, at the same time, an alkaline phosphatase lab value that is less than 2X the upper limit of normal, as determined by way of protocol-specified laboratory testing or unscheduled laboratory testing.*

*Note: These criteria are based upon available regulatory guidance documents. The purpose of the criteria is to specify a threshold of abnormal hepatic tests that must trigger an additional evaluation for an underlying etiology. The trial site guidance for assessment and follow up of these criteria can be found in the Investigator Trial File Binder (or equivalent).

It may also be appropriate to conduct additional evaluation for an underlying etiology in the setting of abnormalities of liver blood tests including AST, ALT, bilirubin, and alkaline phosphatase that do not meet the criteria noted above. In these cases, the decision to proceed with additional evaluation will be made through consultation between the study investigators and the Sponsor Clinical Director. However, abnormalities of liver blood tests that do not meet the criteria noted above are not ECIs for this trial.

1. any suspected allergic reaction, including the following:

- Any skin reaction, skin eruption, and/or rash occurrence in a study subject following administration of study drug,
- Study-drug related systemic reactions or study drug-related hypersensitivity reactions (e.g., anaphylaxis, angioedema).

7.2.4 Evaluating Adverse Events

An investigator who is a qualified physician will evaluate all adverse events with respect to the elements outlined in [Table 7](#). The investigator's assessment of causality is required for each adverse event. Refer to [Table 7](#) for instructions in evaluating adverse events.

Table 7 Evaluating Adverse Events

Maximum Intensity	Mild	awareness of sign or symptom, but easily tolerated (for pediatric trials, awareness of symptom, but easily tolerated)
	Moderate	discomfort enough to cause interference with usual activity (for pediatric trials, definitely acting like something is wrong)
	Severe	incapacitating with inability to work or do usual activity (for pediatric trials, extremely distressed or unable to do usual activities)
Seriousness	A serious adverse event (AE) is any adverse event occurring at any dose or during any use of Sponsor's product that:	
	† Results in death ; or	
	† Is life threatening ; or places the subject, in the view of the investigator, at immediate risk of death from the event as it occurred [Note: This does not include an adverse event that, had it occurred in a more severe form, might have caused death.]; or	
	† Results in a persistent or significant disability/incapacity (substantial disruption of one's ability to conduct normal life functions); or	
	† Results in or prolongs an existing inpatient hospitalization (hospitalization is defined as an inpatient admission, regardless of length of stay, even if the hospitalization is a precautionary measure for continued observation. (Note: Hospitalization for an elective procedure to treat a pre-existing condition that has not worsened is not a serious adverse event. A pre-existing condition is a clinical condition that is diagnosed prior to the use of a Merck product and is documented in the patient's medical history.); or	
	† Is a congenital anomaly/birth defect (in offspring of subject taking the product regardless of time to diagnosis); or	
	Is a cancer (although not serious per ICH definition, is reportable to the Sponsor within 24 hours to meet certain local requirements); or	
	Is associated with an overdose (whether accidental or intentional). Any adverse event associated with an overdose is considered a serious adverse event for collection purposes. An overdose that is not associated with an adverse event is considered a non-serious event of clinical interest and must be reported within 24 hours.	
	Other important medical events that may not result in death, not be life threatening, or not require hospitalization may be considered a serious adverse event when, based upon appropriate medical judgment, the event may jeopardize the subject and may require medical or surgical intervention to prevent one of the outcomes listed previously (designated above by a †).	
Duration	Record the start and stop dates of the adverse event. If less than 1 day, indicate the appropriate length of time and units	
Action taken	Did the adverse event cause the Sponsor's product to be discontinued?	
Relationship to Sponsor's Product	Did the Sponsor's product cause the adverse event? The determination of the likelihood that the Sponsor's product caused the adverse event will be provided by an investigator who is a qualified physician. The investigator's signed/dated initials on the source document or worksheet that supports the causality noted on the AE form, ensures that a medically qualified assessment of causality was done. This initialed document must be retained for the required regulatory time frame. The criteria below are intended as reference guidelines to assist the investigator in assessing the likelihood of a relationship between the test drug and the adverse event based upon the available information The following components are to be used to assess the relationship between the Sponsor's product and the AE ; the greater the correlation with the components and their respective elements (in number and/or intensity), the more likely the Sponsor's product caused the adverse event:	
	Exposure	Is there evidence that the subject was actually exposed to the Sponsor's product such as: reliable history, acceptable compliance assessment (pill count, diary, etc.), expected pharmacologic effect, or measurement of drug/metabolite in bodily specimen?
	Time Course	Did the AE follow in a reasonable temporal sequence from administration of the Sponsor's product? Is the time of onset of the AE compatible with a drug-induced effect (applies to trials with investigational medicinal product)?
	Likely Cause	Is the AE not reasonably explained by another etiology such as underlying disease, other drug(s)/vaccine(s), or other host or environmental factors

Relationship to Sponsor's Product (continued)	The following components are to be used to assess the relationship between the Sponsor's product and the AE: (continued)	
	Dechallenge	Was the Sponsor's product discontinued or dose/exposure/frequency reduced? If yes, did the AE resolve or improve? If yes, this is a positive dechallenge. If no, this is a negative dechallenge. (Note: This criterion is not applicable if: (1) the AE resulted in death or permanent disability; (2) the AE resolved/improved despite continuation of the Sponsor's product; (3) the trial is a single-dose drug trial); or (4) Sponsor's product(s) is/are only used one time.)
	Rechallenge	Was the subject re-exposed to the Sponsor's product in this trial? If yes, did the AE recur or worsen? If yes, this is a positive rechallenge. If no, this is a negative rechallenge. (Note: This criterion is not applicable if: (1) the initial AE resulted in death or permanent disability, or (2) the trial is a single-dose drug trial); or (3) Sponsor's product(s) is/are used only one time.) NOTE: IF A RECHALLENGE IS PLANNED FOR AN ADVERSE EVENT WHICH WAS SERIOUS AND WHICH MAY HAVE BEEN CAUSED BY THE SPONSOR'S PRODUCT, OR IF RE-EXPOSURE TO THE SPONSOR'S PRODUCT POSES ADDITIONAL POTENTIAL SIGNIFICANT RISK TO THE SUBJECT THEN THE RECHALLENGE MUST BE APPROVED IN ADVANCE BY THE SPONSOR CLINICAL DIRECTOR AND THE INSTITUTIONAL REVIEW BOARD/INDEPENDENT ETHICS COMMITTEE.
Consistency with Trial Treatment Profile	Is the clinical/pathological presentation of the AE consistent with previous knowledge regarding the Sponsor's product or drug class pharmacology or toxicology?	
The assessment of relationship will be reported on the case report forms /worksheets by an investigator who is a qualified physician according to his/her best clinical judgment, including consideration of the above elements.		
Record one of the following:	Use the following scale of criteria as guidance (not all criteria must be present to be indicative of a Sponsor's product relationship).	
Yes, there is a reasonable possibility of Sponsor's product relationship.	There is evidence of exposure to the Sponsor's product. The temporal sequence of the AE onset relative to the administration of the Sponsor's product is reasonable. The AE is more likely explained by the Sponsor's product than by another cause.	
No, there is not a reasonable possibility of Sponsor's product relationship	Subject did not receive the Sponsor's product OR temporal sequence of the AE onset relative to administration of the Sponsor's product is not reasonable OR the AE is more likely explained by another cause than the Sponsor's product. (Also entered for a subject with overdose without an associated AE.)	

